Bilirubin ≥ 2 x ULN, serum creatinine ≥ 3 x ULN or calculated creatinine clearance < 50 mL/min	Delay for up to 3 weeks until recovery of bilirubin ≥ 2 x ULN or serum creatinine ≥ 3 x ULN. Reduce subsequent doses by one dose level. Discontinue subject if already at the lowest dose level or if subject has not recovered in 3 weeks.
All other clinically relevant toxicities ≥ Grade 3	Delay for up to 3 weeks until recovery to ≤ Grade 1 toxicity. Reduce subsequent doses by one dose level. Discontinue subject who continues to experience ≥ Grade 3 toxicity despite dose reduction. Discontinue subject if already at the lowest dose level or if subject has not recovered in 3 weeks.
Abbreviations: C = cycle; D = Day; K ⁺ = potassium; TLS = tumor lysis syndrome; ULN = upper limit of normal.	

Table 10 Dinaciclib Dose

Dose of Dinaciclib at Time of Adverse Event Requiring Dose Reduction	Dose to use for Next Dose
14 mg/m ²	10 mg/m ²
10 mg/m ²	7 mg/m ²
7 mg/m ²	discontinue

For a subject who has had dose reductions, dose escalation of dinaciclib to the next dose level is permitted provided that the subject remains on trial after receiving 2 additional cycles of combination treatment without \geq Grade 2 toxicity and upon consultation with sponsor.

Tumor Lysis Syndrome

The Cairo and Bishop criteria will be used to define TLS (Section 12.5) [31].

Using the Cairo-Bishop definition of laboratory TLS, K, calcium (Ca), phosphorus (P), and uric acid will be evaluated at 3 and 5 hours after the start of the first dinaciclib infusion (Cycle 1 Day 1) as part of a TLS work-up (Section 12.5). Subjects with a positive TLS work-up should remain in the hospital and follow-up should be initiated. If necessary, subjects must be admitted overnight for observation.

TLS is defined as any 2 of the following serum levels within 3 days before or 7 days after initiation of dinaciclib, assuming adequate hydration and administration of a hypo-uremic:

- Uric acid levels of $> 476 \mu\text{mol/L}$ (8 mg/dL), or a 25% increase from Baseline
- Potassium (K⁺) levels of $> 6 \text{ mmol/L}$ (6 mEq/L), or a 25% increase from Baseline
- Phosphorus levels of $> 1.45 \text{ mmol/L}$ (4.5 mg/dL), or a 25% increase from Baseline
- Calcium levels of $< 1.75 \text{ mmol/L}$ (7 mg/dL), or a 25% decrease from Baseline

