Response will be determined locally according to IMWG criteria [2] described in Section 12.8.

7.1.2.8.2.2 Imaging for Subjects with Myeloma Bone Disease

Skeletal survey by conventional radiography must be performed at screening within 28 days of Cycle 1 Day 1 to determine the extent of the subject's myeloma bone disease. The use of conventional or low dose CT scan or magnetic resonance imaging (MRI) bone survey is acceptable. A skeletal survey performed as standard of care prior to signing consent can be used for screening if performed within 28 days of Cycle 1 Day 1.

During the course of the trial, skeletal surveys should be performed as clinically indicated. If suspected disease progression, the same modality of imaging used at screening should be performed for assessment of progression. The development of a compression fracture does not necessarily exclude antitumor response if not related to disease progression. Bone lesions should be considered as non-measurable disease and recorded as such.

For subjects with extramedullary soft tissue plasmacytomas, an MRI, CT, or positron emissions tomography (PET)/CT should be performed at baseline within 28 days of Cycle 1 Day 1. An MRI, CT, or PET/CT performed as standard of care prior to signing consent can be used for screening if performed within 28 days of Cycle 1 Day 1. During the course of the trial, subsequent imaging should be performed as clinically indicated (whether or not an

extramedullary soft tissue plasmacytoma was present at baseline) and at the time of a CR or stringent CR (sCR) assessment. The same modality of imaging used at screening should be performed for subsequent assessments.

At any time a subject develops bone pain or there is a suspicion of new bone disease or extramedullary soft tissue plasmacytoma indicative of disease progression, appropriate imaging according to clinical practice should be performed to confirm disease progression.

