7.1.3.1 Laboratory Safety Evaluations (Hematology, Chemistry and Urinalysis)

Laboratory tests for hematology, chemistry, and urinalysis are specified in [Table 16](#). Except for analyses of biomarkers or other prognostic indicators (proteomics, genetics, transcriptional analysis, pharmacokinetics, antibodies), all tests will be analyzed locally.

Table 16 Laboratory Tests

Hematology	Chemistry	Urinalysis	Other
Hematocrit	Albumin	Blood	Pregnancy test (serum or urine) ^a
Hemoglobin	Alkaline phosphatase	Glucose	PT/INR
Platelet count	Alanine aminotransferase	Protein	aPTT
WBC (total and differential) ^d	Aspartate aminotransferase	Specific gravity	Total T3 or free T3, FT4, and TSH ^b
RBC	Bicarbonate ^c	Microscopic exam, if abnormal results are noted	B2 microglobulin G6PD (as necessary)
Absolute lymphocyte count ^d	Calcium		
	Chloride		
Absolute neutrophil count ^d	Creatinine		
	Glucose		
	LDH		
	Phosphorus		
	Potassium		
	Sodium		
	Total bilirubin		
	Direct bilirubin		
	Total protein		
	Uric Acid		
	Blood urea nitrogen		

^a Perform on women of childbearing potential only 72 hours prior to Day 1 of Cycle 1. All women who are being considered for participation in the trial, and who are not surgically sterilized or postmenopausal, must be tested for pregnancy within 72 hours of each cycle of trial treatment and 30 days post-treatment.

^b T3 is preferred; if not available free T3 may be tested.

^c If this test is not done as part of local standard of care, this test does not need to be performed.

^d Report % or absolute results per standard of practice. Report the results in the same manner throughout the trial.

Abbreviations: aPTT = activated partial thromboplastin time; G6PD = glucose-6-phosphate dehydrogenase deficiency; INR = international normalized ratio; LDH = lactic dehydrogenase; PT = prothrombin time; RBC = red blood cells; WBC = white blood cells.

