Progressive disease ^a To be used for calculation of time to progression and progression-free survival end points for all patients including those in CR (includes primary progressive disease and disease progression on or off therapy)	Laboratory or Biochemical Relapse or Progressive Disease: requires any one or more of the following: Increase of $\geq 25\%$ from baseline in Serum M-component and/or (the absolute increase must be ≥ 0.5 g/dl) ^b Urine M-component and/or (the absolute increase must be ≥ 200 mg/24 h Only in patients without measurable serum and urine M-protein levels: the difference between involved and uninvolved FLC levels. The absolute increase must be >10 mg/dl. Bone marrow plasma cell percentage: the absolute % must be $\geq 10\%$ ^c Definite development of new bone lesions or soft tissue plasmacytomas or definite increase in the size of existing bone lesions or soft tissue plasmacytomas Development of hypercalcemia (corrected serum calcium > 11.5 mg/dl or 2.65 mmol/l) that can be attributed solely to the plasma cell proliferative disorder
Clinical relapse (i.e., progressive disease requiring re-treatment or alternate treatment) ^b	Clinical relapse or progressive disease requires one or more of: Direct indicators of increasing disease and/or end organ dysfunction (CRAB features) ^b It is not used in calculation of time to progression or progression-free survival but is listed here as something that can be reported optionally or for use in clinical practice 1. Development of new soft tissue plasmacytomas or bone lesions 2. Definite increase in the size of existing plasmacytomas or bone lesions. A definite increase is defined as a 50% (and at least 1 cm) increase as measured serially by the sum of the products of the cross-diameters of the measurable lesion 3. Hypercalcemia (>11.5 mg/dl) [2.65 mmol/l] 4. Decrease in hemoglobin of ≥ 2 g/dl [1.25 mmol/l] (see Table 3 for further details) 5. Rise in serum creatinine by 2 mg/dl or more [177 μ mol/l or more]
Relapse from CR ^a (To be used only if the end point studied is DFS) ^d	Any one or more of the following: Reappearance of serum or urine M-protein by immunofixation or electrophoresis Development of $\geq 5\%$ plasma cells in the bone marrow ^c Appearance of any other sign of progression (i.e., new plasmacytoma, lytic bone lesion, or hypercalcemia see below)

Abbreviations: CR, complete response; DFS, disease-free survival.

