^a All relapse categories require two consecutive assessments made at anytime before classification as relapse or disease progression and/or the institution of any new therapy.

^b For progressive disease, serum M-component increases of ≥ 1 gm/dl are sufficient to define relapse if starting M-component is ≥ 5 g/dl.

^c Relapse from CR has the 5% cutoff versus 10% for other categories of relapse.

^d For purposes of calculating time to progression and progression-free survival, CR patients should also be evaluated using criteria listed above for progressive disease.

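### The myeloma progression criterion gives one calcium limit as 11.5 mg/dL or 2.65 mmol/L, but by the protocol's own conversion 2.65 mmol/L is 10.6 mg/dL

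*Combined protocol and SAP*

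**What the plan says.** Section 12.8 reproduces the myeloma response and progression criteria. In its Table 6, the progressive disease row needs any one of several findings. One of them is "Development of hypercalcemia (corrected serum calcium > 11.5 mg/dl or 2.65 mmol/l"), qualified by the words "that can be attributed solely to the plasma cell proliferative disorder". That row is the one that counts for the endpoint: "To be used for calculation of time to progression and progression-free survival end points for all patients including those in CR". A footnote adds a condition: "All relapse categories require two consecutive assessments made at anytime before classification as relapse or disease progression". The Clinical relapse row repeats the pair as "Hypercalcemia (>11.5 mg/dl) [2.65 mmol/l"], but the table says that this row does not enter time to progression or PFS.

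Section 5.2.1.3.3 gives calcium in both units once more, in the definition of tumor lysis syndrome: "Calcium levels of $< 1.75 \text{ mmol/L}$ (7 mg/dL), or a 25% decrease from Baseline".

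The criteria are applied at the sites. Under Myeloma Laboratory Testing Disease Measurements (7.1.2.8.2.1) the protocol states: "Response will be determined locally according to IMWG criteria [2] described in Section 12.8". Calcium is in the chemistry panel of Table 16. Section 7.1.3.1 says of the tests there, apart from biomarker and similar analyses, that "all tests will be analyzed locally". No section says which calcium unit governs.

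**The concern.** Two figures joined by *or*, with different units, read as one limit written twice. If they are not equal, an investigator whose laboratory reports mmol/L applies a different progression threshold from one whose laboratory reports mg/dL. Taking *or* literally does not help: the lower limit would then always decide, and the 11.5 mg/dL figure would never operate.

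Progression is the PFS event and one of the two events that end DOR (Section 8.4.1; Tables 18 and 19). Both endpoints are by investigator assessment, and nothing in the plan would show afterwards that a call had turned on the unit. With the mmol/L figure, progression would be called at a lower calcium, and so possibly earlier, than with the mg/dL figure.

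**Working it through.** **Inputs.** Stated limit: 11.5 mg/dL or 2.65 mmol/L (Section 12.8, Table 6). Conversion pair: 7 mg/dL and 1.75 mmol/L (Section 5.2.1.3.3).

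**1. Factor in the protocol.** 7 / 1.75 = 4.0 mg/dL per mmol/L.

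**2. Attempt to reproduce the stated pair.** The pair needs 11.5 / 2.65 = 4.34 mg/dL per mmol/L. It is not reproduced by 4.0.

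**3. Each limit in the other unit.**
- 2.65 × 4.0 = 10.6 mg/dL
- 11.5 / 4.0 = 2.875 mmol/L
- Gap: 11.5 − 10.6 = 0.9 mg/dL, or 2.875 − 2.65 = 0.225 mmol/L. As a share of the mg/dL limit, 0.9 / 11.5 = about 8%.

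**4. Can rounding explain it?**
- If the 7 and the 1.75 are rounded in their last places as 6.95–7.05 and 1.745–1.755, the factor lies between 6.95 / 1.755 = 3.96 and 7.05 / 1.745 = 4.04.
- If the 7 is rounded to a whole number (6.5–7.5), the factor lies between 6.5 / 1.755 = 3.70 and 7.5 / 1.745 = 4.30. The required 4.34 is outside even this range.
- Letting 2.65 be as high as 2.655 as well, 2.655 × 4.298 = 11.41 mg/dL, still below 11.5.
- Cross-check, assuming an atomic mass of about 40.08 for calcium (not a figure from the documents): factor 4.008, so 2.65 mmol/L is 10.62 mg/dL and 11.5 mg/dL is 2.87 mmol/L. The conclusion is unchanged.

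**5. Where the two limits disagree** (factor 4.0):

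| Corrected calcium, mg/dL | mmol/L | Above 11.5 mg/dL? | Above 2.65 mmol/L? |
|---|---|---|---|
| 10.5 | 2.625 | no | no |
| 10.7 | 2.675 | no | yes |
| 11.0 | 2.75 | no | yes |
| 11.4 | 2.85 | no | yes |
| 11.6 | 2.90 | yes | yes |

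The limits disagree for values above 10.6 and up to 11.5 mg/dL, and agree elsewhere.

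**The case against.** The case on the other side accepts the arithmetic and disputes the consequence. Most of it stands.

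- **A calcium in the band is not progression by itself.** It must be attributed solely to the myeloma and seen on two consecutive assessments. This stands. The unit decides only whether the threshold is met.
- **Calcium will rarely decide alone.** Entry required measurable serum or urine M-protein or involved free light chain (inclusion criterion 13). Non-secretory and oligo-secretory disease was excluded (exclusion criterion 22), and response is assessed every cycle after Cycle 1. Progression would usually show through another criterion first. This stands.
- **The cohort is closed.** rrMM enrollment stopped on 07-AUG-2017, its subjects came off treatment, and those remaining are in survival follow-up. The effect is on how progression was classified in the past. This stands.
- **Mixed units are not shown.** A reader might infer that US and non-US sites used different limits, because testing is local and Section 8.10 plans a regional subgroup. No section gives any site's reporting unit, so the documents do not support that as fact.
- **Treatment stopping.** A reader might also infer that subjects were taken off treatment according to the unit. Sections 7.1.2.7.2 and 7.1.2.7.3 let a clinically stable subject continue after progression. Section 5.8.1 lists confirmed radiographic progression, with a Sponsor exception, although another item there covers any progression of a malignancy. Stopping does not follow mechanically from the calcium limit.
- **Little statistical weight.** PFS and DOR are secondary Kaplan-Meier summaries with no formal hypothesis (Section 8.3, Table 19), and DOR covers responders only, in a cohort closed for lack of efficacy. This stands as a limit on size.
- **The table is presented as taken from a publication.** Whether the pair comes from there cannot be checked from the documents. It would not cure the problem, because Section 12.8 is the text that sites apply. It is a reason for the sponsor, and not this review, to decide which figure is kept.

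None of this makes the two figures equal or names a governing unit.

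**Conclusion.** Wrong as written. The progressive disease row of Section 12.8 contains two calcium limits, 10.6 and 11.5 mg/dL on the protocol's own conversion, where one is meant. The duplicate under Clinical relapse has the same fault but does not feed PFS.

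An effect on results needs all of the following: sites reporting calcium in different units (assumed, not documented), a corrected calcium inside the band, sole attribution to myeloma, confirmation on two consecutive assessments, and no other progression criterion met by then. About 30 rrMM subjects were planned for Signal Detection, and the number actually enrolled is not given. The number affected is probably few and may be zero.

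The documents do not support saying that the myeloma PFS or DOR results are biased, or that either figure is the correct one. They support saying that the endpoint definition is inconsistent, and that its effect can be checked while the myeloma PFS and DOR summaries remain planned (Section 8.6, Table 19).

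**What to change.** 1. In Section 12.8, reconcile the mg/dL and mmol/L figures in both the progressive disease and the Clinical relapse entries, and state one governing limit. The sponsor should choose it and record the reason.
2. Before the final rrMM PFS and DOR summaries, convert local calcium values to one unit. Flag each investigator progression call, or absence of one, that rests on calcium alone with a corrected value above 10.6 and up to 11.5 mg/dL.
3. Leave investigator-assessed progression unchanged as the endpoint. Report the flagged cases in a sensitivity listing that shows the progression date under each limit, and state if there are none.
4. Document this in the supplemental statistical analysis plan, which Section 8.0 provides for changes made before final database lock.

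The cost is a corrected pair of figures in two table entries and one programmed listing. Calcium and albumin are both in Table 16, so the values should already be held. The protocol gives no formula for corrected calcium, so the listing should state which was used.

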12.9 Lymphoma Disease Response Criteria

Cheson et al. Revised Response Criteria for Malignant Lymphoma. *J Clin Oncol.* 2007; 25:579-586.

Criteria for lymphoma disease assessment:

Table 2. Response Definitions for Clinical Trials				
Response	Definition	Nodal Masses	Spleen, Liver	Bone Marrow
CR	Disappearance of all evidence of disease	(a) FDG-avid or PET positive prior to therapy; mass of any size permitted if PET negative (b) Variably FDG-avid or PET negative; regression to normal size on CT	Not palpable, nodules disappeared	Infiltrate cleared on repeat biopsy; if indeterminate by morphology, immunohistochemistry should be negative
PR	Regression of measurable disease and no new sites	> 50% decrease in SPD of up to 6 largest dominant masses; no increase in size of other nodes (a) FDG-avid or PET positive prior to therapy; one or more PET positive at previously involved site (b) Variably FDG-avid or PET negative; regression on CT	> 50% decrease in SPD of nodules (for single nodule in greatest transverse diameter); no increase in size of liver or spleen	Irrelevant if positive prior to therapy; cell type should be specified
SD	Failure to attain CR/PR or PD	(a) FDG-avid or PET positive prior to therapy; PET positive at prior sites of disease and no new sites on CT or PET (b) Variably FDG-avid or PET negative; no change in size of previous lesions on CT		
Relapsed disease or PD	Any new lesion or increase by > 50% of previously involved sites from nadir	Appearance of a new lesion(s) > 1.5 cm in any axis, > 50% increase in SPD of more than one node, or > 50% increase in longest diameter of a previously identified node > 1 cm in short axis Lesions PET positive if FDG-avid lymphoma or PET positive prior to therapy	> 50% increase from nadir in the SPD of any previous lesions	New or recurrent involvement

Abbreviations: CR, complete remission; FDG, [¹⁸F]fluorodeoxyglucose; PET, positron emission tomography; CT, computed tomography; PR, partial remission; SPD, sum of the product of the diameters; SD, stable disease; PD, progressive disease.

12.10 Lymphoma B Symptoms and Constitutional Symptoms

Lymphoma B Symptoms:

Lymphoma B symptoms are a set of clinical criteria used in the initial diagnosis and treatment of Hodgkin Lymphoma. These criteria are used in this trial as part of the initial assessment of Lymphoma disease staging and as a measure of the response to trial treatment.

The criteria are as follows:

- Unexplained weight loss of more than 10% of the body weight during the 6 months before initial staging investigation;
- Unexplained, persistent, or recurrent fever with temperatures above 38°C during the previous month; and
- Recurrent drenching night sweats during the previous month.

Source: Lister TA, Crowther D, Sutcliffe, SB, et al. Report of a committee convened to discuss the evaluation and staging of patients with Hodgkin's disease: Cotswolds meeting. *J Clin Oncol* 1989;7:1630-1636.

Constitutional Symptoms:

For all subjects with CLL, constitutional symptoms should be assessed at the time points described in Section 6.0 and Section 7.1.3.3.

Constitutional symptoms, defined as any one or more of the following disease-related symptoms or signs:

- Unintentional weight loss of 10% or more within the previous 6 months;
- Significant fatigue (ie, ECOG PS 2 or worse; inability to work or perform usual activities);
- Fevers higher than 100.5°F or 38.0°C for 2 or more weeks without other evidence of infection; or
- Night sweats for more than 1 month without evidence of infection.

Source: Hallek M, Cheson BD, Catovsky D, et al. Guidelines for the diagnosis and treatment of chronic lymphocytic leukemia: a report from the International Workshop on Chronic Lymphocytic Leukemia updating the National Cancer Institute-Working Group 1996 guidelines. *Blood*. 2008 Jun 15; 111(12): 5446-5456.

12.11 Common Terminology Criteria for Adverse Events V4.0

The descriptions and grading scales found in the revised NCI Common Terminology Criteria for Adverse Events (CTCAE) version 4.0 will be used for AE reporting. (<http://ctep.cancer.gov/reporting/ctc.html>).

12.12 Abbreviations

Abbreviation/Term	Definition
ABC	activated B-cell-like
ADA(s)	antidrug antibody(ies)
AE(s)	adverse event(s)
ALT	alanine transaminase
ANC	absolute neutrophil count
aPTT	activated partial thromboplastin time
ASaT	all subjects as treated
AST	aspartate aminotransaminase
β -hCG	beta-human chorionic gonadotropin
BID	twice daily
BCL2	B-cell lymphoma 2
Ca	calcium
CBC	complete blood count
CD	cluster of differentiation
CDK	cyclin-dependent kinase
CFR	Code of Federal Regulations
CI	principal coordinator
CLL	chronic lymphocytic leukemia
CR	complete remission
CRS	cytokine release syndrome
CSR	clinical trial report
CT	computed tomography
CTCAE	Common Toxicity Criteria for Adverse Events
CTLA-4	cytotoxic T-lymphocyte-associated antigen-4
CYP3A4	cytochrome P450 3A4
DLBCL	diffuse large B cell lymphoma
DLT	dose-limiting toxicities
DNA	deoxyribonucleic acid
DOR	duration of response

Abbreviation/Term	Definition
ECI	events of clinical interest
ECOG	Eastern Cooperative Oncology Group
EDC	electronic data capture
EMEA	European Medicines Evaluation Agency
FDA	Food and Drug Administration
FDAAA	Food and Drug Administration Amendments Act
FDAMA	Food and Drug Administration Modernization Act
FDG	fluorodeoxyglucose
FIH	first in human
FISH	fluorescence in situ hybridization
FLC	free light chain
G6PD	glucose-6-phosphate dehydrogenase deficiency
GCB	germinal center B-cell-like
GCP	Good Clinical Practice
G-CSF	granulocyte colony stimulating factor
GFR	glomerular filtration rate
GI	gastrointestinal
HBsAg	hepatitis B surface antigen
HCV	Hepatitis C virus
HIV	Human immunodeficiency virus
IB	Investigator's Brochure
ICH	International Council on Harmonization
Ig	immunoglobulin
IgG4	immunoglobulin G4
IgVH	immunoglobulin heavy chain
IMiD	pomalidomide, lenalidomide, or thalidomide
IMWG	International Myeloma Working Group criteria for response assessment in multiple myeloma
INR	International normalized ratio
irAE	immune-related adverse events
IRBs/ERCs	institutional review boards/ethics committees

Abbreviation/Term	Definition
ITSM	immunoreceptor tyrosine-based switch motif
IUD	intrauterine device
IV	intravenous
IVRS/IWRS	interactive voice response system/ integrated web response system
iwCLL	International Workshop on Chronic Lymphocytic Leukemia
K	potassium
mAb	monoclonal antibody
MM	multiple myeloma
MRI	magnetic resonance imaging
mRNA	messenger ribonucleic acid
MSD	Merck Sharp & Dohme Corp., a subsidiary of Merck & Co., Inc.
NHL	non-Hodgkin lymphoma
NSAID(s)	non-steroidal anti-inflammatory drugs
ORR	objective response rate
OS	overall survival
P	phosphorus
PBPK	physiologically based pharmacokinetic
PD	progressive disease
PD-1	programmed cell death-1
PD-L1	programmed death-ligand 1
PD-L2	programmed death-ligand 2
PET	positron-emission tomography
PFS	progression-free survival
PK	pharmacokinetics
PO, po	orally
POEMS syndrome	plasma cell dyscrasia with polyneuropathy, organomegaly, endocrinopathy, monoclonal protein, and skin changes
PR	partial remission
PT	prothrombin time
PTT	partial thromboplastin time

Abbreviation/Term	Definition
Q2W	every 2 weeks
Q3W	every 3 weeks
RNA	ribonucleic acid
RPTD	recommended Phase 2 dose
rrCLL	relapsed or refractory chronic lymphocytic leukemia
rrDLBCL	relapsed or refractory diffuse large B-cell lymphoma
rrMM	relapsed or refractory multiple myeloma
SAE(s)	serious adverse event(s)
sCR	stringent complete remission
SCT	stem cell transplant
SPEP	serum M protein by electrophoresis
T1DM	type 1 diabetes mellitus
T3	triiodothyronine
Tregs	regulatory T cells
TLS	tumor lysis syndrome
ULN	upper limit of normal
UPEP	urine M protein by electrophoresis

